## **I. Hypotheses and Specific Aims**

### Hypotheses

- 1) Shingrix (RZV) recipients will have a lower rate of varicella-zoster virus (VZV) DNAemia after a live intradermal (ID) VZV challenge (vOka vaccine) than Zostavax (ZVL) recipients because of higher and/or more rapid VZV-specific T cell responses.
- 2) After a live VZV ID challenge, RZV recipients will have the same rate of VZV DNAemia whether the challenge was performed <1 or >5 years after vaccination; whereas ZVL recipients will have lower rates of VZV DNAemia if they are challenged <1 year after vaccinations compared with >5 years.
- 3) The peak memory VZV and/or gE Th1 responses to RZV mediate protective immune responses conferred by RZV against VZV DNAemia after VZV ID challenge; early responses may also play a role

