**Exclusion Criteria**

1. Inability or unwillingness of a participant to give written informed consent or to comply with study protocol.
2. Prior history of HZ;
3. Known history of hypersensitivity to ZVL or vaccine components in all study candidates and to hypersensitivity to RZV or vaccine components in Cohort 4.
4. Known neomycin contact allergy or other ZVL components such as gelatin.
5. Untreated anemia in Cohorts 1 and 2.
6. Blood products received in the 3 months prior to study enrollment or planned for the subsequent week for Part A; Part B requires the same exclusion but extends it to the week after the vOka challenge, which is 6 months after completing ZVL or RZV administration.
7. Any confirmed or suspected immunosuppressive or immunodeficient condition resulting from disease (e.g., malignancy, HIV), or immunosuppressive/cytotoxic therapy.
8. Use, or anticipated use, of immunosuppressants or other immune-modifying drugs during the period starting 30 days prior to ID ZVL challenge through 7 days after. This includes chronic administration of corticosteroids (>14 consecutive days of prednisone at a dose of  $\geq$  20 mg/day [or equivalent], long-acting immune-modifying agents, or immunosuppressive/cytotoxic therapy (e.g., medications used during cancer chemotherapy or to treat autoimmune disorders). *Topical, ophthalmic, intra-articular, or inhaled/nebulized steroids are allowed.*
9. Concomitant vaccine received within 2 (inactive) or 4 (live) weeks prior to the study for subjects in all Cohorts, and during the first week of the study. For subjects in Cohorts 3 and 4, no concomitant vaccine received within 2 (inactive) or 4 (live) weeks prior to ID vOka and for the following 7 days.
10. Women of child-bearing potential.
11. Pregnancy or breast-feeding.
12. Participation in a concurrent clinical study in which the subject will be exposed to an investigational product (drug or vaccine) during the period starting 7 days before the first dose of study vaccine through the completion of the study.
13. Antivirals with activity against VZV, including acyclovir, valacyclovir, ganciclovir, valganciclovir, foscarnet, cidofovir, brincidofovir and penciclovir within 7 days of the ID ZVL challenge.

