### **Part B; Cohorts 3 and 4 – No Previous HZ vaccine**

Part B measures VZV DNAemia and systemic VZV-specific immune responses after ID vOka challenge in individuals who received HZ vaccines 6 months prior to the injection.

**Cohort 3** (n=35) subjects will be vaccinated with ZVL at enrollment; blood will be obtained at Days 0, 1, 3, 7 and 30 days after. Five - six months after receiving ZVL subject will be challenged with vOka administration (as described in Part A) followed by visits 1, 3, and 7 days later at which blood is drawn. Total of 9 to 11 visits.

These subjects will also be offered RZV vaccine (to comply with ACIP recommendations for shingles immunization) to be administered  $\geq$  60 days after vOka challenge. If subject wishes to receive the RZV vaccine, 2 additional visits will be required 2 beginning 2 months after Visit 6, increasing the duration of participation up to 10 months. Subjects will not be reimbursed for these visits but will receive the vaccine free of charge.

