### **Schedule of Events – Cohort 3**

Cohort 3 – No Previous HZ Vaccine (to be admin ZVL)	Visit 1	Visit 2	Visit 3	Visit 4	Phone	Visit 5	Visit 6	Visit 7	Visit 8	Visit 9	Phone	Visit 10	Visit 11
	Day 0	Day 1	Day 3	Day 7	Day 9 (+3)	Day 30 (+7)	Day 150 (+44)	Day 151	Day 153 (+2)	Day 157 (+10)	+48 hours	60 Days after V6 (+30)	60 days after V10 (+30)
Informed consent, review of eligibility criteria	●												
Medical history and current medications	●						●						
Blood draw (60ml)	●	●	●	●		●	●	●	●	●			
Pre-vaccination body temperature	●						●						
Vaccination – Zostavax	●												
Vaccination (ID vOka challenge)							●						
AE assessment	●	●	●	●	●	●	●	●	●	●			
Vaccination – Dose 1 RZV 											● 		
Vaccination – Dose 2 RZV 												● 	

If subject wishes to receive RZV

**Cohort 4** (n=35) subjects will be enrolled, have blood (60ml) drawn, and will be administered RZV (2 doses –D0, D60) prepared and administered in accordance with the package insert, in the clinic. Participation will consist of 10 visits over the course of approximately 9 months. Blood will be drawn at Day 0, Days 61, 63, 67, and 90. These subjects will receive the challenge dose of vOka 6 months later at Day 240, with blood drawn, then drawn again at Days 241, 243, 247. Participation will consist of 10 visits over the course of approximately 8.5 months.

### Schedule of Events – Cohort 4

Cohort 4 – No Previous HZ Vaccine (to be admin RZV)	Visit 1	Phone	Visit 2	Visit 3	Visit 4	Visit 5	Visit 6	Visit 7	Visit 8	Visit 9	Visit 10	Phone
	Day 0	Day 7 (+3)	Day 60 (+14)	Day 61	Day 63	Day 67 (+3)	Day 90 (+7)	Day 240 (+14)	Day 241	Day 243	Day 247 (+3)	+48 hours after V 5, 6, 10
Informed consent, review of eligibility criteria	●											
Medical history and current medications	●		●					●				
Blood draw (60ml)	●		●	●	●	●	●	●	●	●	●	
Pre-vaccination body temperature	●		●					●				
Vaccination – Dose 1 RZV	●											
Vaccination – Dose 2 RZV			●									
Vaccination (ID vOka challenge)								●				
AE assessment	●	●	●	●	●	●	●	●	●	●	●	

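### The concomitant-vaccine restriction covers study entry and the vOka challenge but not RZV dose 2, after which Cohort 4's pre-challenge response samples are drawn

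*Combined protocol and SAP*

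**What the plan says.** Exclusion 9 in Section IV.B sets two windows.

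- **Study entry, all cohorts.** No other vaccine in the 2 (inactive) or 4 (live) "weeks prior to the study for subjects in all Cohorts, and during the first week of the study".
- **Challenge, Cohorts 3 and 4.** The rule is "no concomitant vaccine received within 2 (inactive) or 4 (live) weeks prior to ID vOka and for the following 7 days".

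The two Part B cohorts in Section IV.C are sampled on different clocks. Cohort 3 receives ZVL at enrolment, and "blood will be obtained at Days 0, 1, 3, 7 and 30 days after". Cohort 4 receives RZV on Days 0 and 60, and its paragraph says "Blood will be drawn at Day 0, Days 61, 63, 67, and 90". The Cohort 4 schedule table adds a draw at Visit 2 (Day 60). Cohort 4 then has the "challenge dose of vOka 6 months later at Day 240, with blood drawn, then drawn again at Days 241, 243, 247".

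Exclusion 9 does not mention RZV dose 2.

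**The concern.** The entry window suits a cohort vaccinated once on Day 0 and sampled intensively in the following week. Cohort 4 is not such a cohort: its only draw in the first study week is the Day 0 baseline, and its 1-, 3- and 7-day sampling starts from dose 2. A participant could receive an influenza vaccine on Day 58 or Day 62 and still comply with the criterion.

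Early cytokine, transcript, epigenetic and general cell-phenotype readouts are not specific to VZV or gE. Another vaccine a few days earlier can move them, and the change would be read as a response to RZV. The note to Secondary Objective 3 (Section I) includes transcript and epigenetic changes after vaccination, and Hypothesis 3 allows a role for early responses. That is the part of the study at stake. Because the matching early draws in Cohort 3 are protected, comparing the two vaccines' early responses would set a protected block against an unprotected one.

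**Working it through.** **1. Confirm the draw days.** Section IV.D gives 60 ml per draw and totals of 600 ml (Cohort 4) and 540 ml (Cohort 3).

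- Cohort 4, schedule table: Days 0, 60, 61, 63, 67, 90, 240, 241, 243, 247. 10 × 60 = 600 ml, as stated.
- Cohort 4, text without Day 60: 9 × 60 = 540 ml, which does not match. The Day 60 draw is therefore counted as real.
- Cohort 3: Days 0, 1, 3, 7, 30, 150, 151, 153, 157. 9 × 60 = 540 ml, as stated.

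**2. Place the windows, using nominal days.** The first study week is taken as Days 0 to 7. Cohort 4's challenge window starts at 240 − 14 = Day 226 (inactive) or 240 − 28 = Day 212 (live) and ends at 240 + 7 = Day 247. Even the latest permitted Day 90 visit (90 + 7 = Day 97) falls well before it.

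**3. Map the draws onto the windows.**

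| Block | Cohort 3 | Cohort 4 |
|---|---|---|
| Day 0 baseline | protected | protected |
| Dose-2 visit | none | Day 60: not protected |
| 1, 3, 7 days after the sampled dose | Days 1, 3, 7: protected | Days 61, 63, 67: not protected |
| About 30 days after | Day 30: not protected | Day 90: not protected |
| Challenge | Days 150, 151, 153, 157: protected | Days 240, 241, 243, 247: protected |

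The like-for-like count leaves out the vaccination-day draw in both cohorts. Before challenge, Cohort 3 has 3 of 4 post-vaccination draws protected and Cohort 4 has 0 of 4.

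**4. Look for another rule that closes the gap.**

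- Exclusion 12 runs to the end of the study but covers only investigational products in a concurrent study.
- Exclusion 14 concerns medical problems and findings, at the investigator's discretion.
- Visit 2 takes a medication history, and Section IV.E has participants asked at each visit about health changes and new medications. A vaccination might surface there, but nothing requires it to be recorded as such or says how to handle it.
- Section IV.G does not address intercurrent vaccines.

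**5. Anchor the existing window to dose 2.** It would run from 60 − 14 = Day 46 (inactive) or 60 − 28 = Day 32 (live) to 60 + 7 = Day 67. That covers Days 60, 61, 63 and 67, so the like-for-like count becomes 3 of 4 in both cohorts. Day 90 stays outside, as Day 30 does in Cohort 3.

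**The case against.** The gap in the text is hard to dispute; the case on the other side is about consequence, and much of it stands.

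- **All post-RZV samples.** A reader might infer that no Cohort 4 sample after RZV is protected. Days 240 to 247 also follow RZV, and exclusion 9 covers them. The primary endpoint, DNAemia after challenge, is measured in that protected period.
- **Antigen-specific readouts.** The core of Hypothesis 3 is that "The peak memory VZV and/or gE Th1 responses to RZV mediate protective immune responses conferred by RZV". Those responses, and the exploratory tetramer work, are antigen-specific, so an unrelated vaccine should largely leave them alone.
- **Mediation analysis.** A reader might infer that contaminated samples feed the mediation models. Section IV.G describes mediators as lying between virus challenge and DNAemia, and nowhere names the Day 61 to 67 samples as inputs. The natural reading is challenge-period data.
- **One-sided bias.** The asymmetry holds only for the early draws. Secondary Objective 3 concerns responses to RZV, so the contrast with Cohort 3 is not central to it. Nothing in the documents ties other vaccinations to later DNAemia, so added noise is the likelier effect.
- **Frequency.** No rate is given. If, by assumption, everyone had one inactive vaccine a year and dose-2 dates were spread evenly, a window of 14 + 7 = 21 days would catch 21/365 = 5.8%, or 35 × 0.058 = 2.0 participants. At 50% to 70% uptake that is 1.0 to 1.4. If dose 2 clustered in influenza season and 10% to 20% were affected, it would be 3.5 to 7 of 35. None of these rates has support in the documents.

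These points narrow the concern but do not remove it. A rule followed to the letter still allows another vaccine within days of the early post-RZV samples.

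**Conclusion.** The concern holds in a limited form. Exclusion 9 leaves Cohort 4's dose-2 sampling block outside both windows: 0 of 4 pre-challenge response draws protected, against 3 of 4 in Cohort 3, with the draw about 30 days after vaccination unprotected in both. This rests on nominal visit days and on reading the first study week as Days 0 to 7.

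What is exposed is the early, non-antigen-specific part of Hypothesis 3 and Secondary Objective 3. The documents do not support a claim that the primary comparison, the challenge-period samples or the mediation results are compromised. The size of the effect is unknown; the illustrative range of about 1 to 7 of 35 participants depends wholly on assumed rates. The point still merits correction, because a clean early sample cannot be taken again later.

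**What to change.** 1. Reconcile exclusion 9 with the Cohort 4 sampling schedule, so that the window already used around Day 0 and the challenge also addresses the dose-2 sampling block. Leave the timing of dose 2 as it is.
2. Record any intercurrent vaccine, with its date, at Visits 2 to 6, using the existing medication history and health-change questions. Asking at Visit 2 alone is not enough: it cannot catch a vaccine given on Day 62.
3. Pre-specify in Section IV.G that Day 60 to 67 samples taken inside that window after another vaccine are set aside, or flagged in a sensitivity analysis, for the non-antigen-specific early-response analyses. For a vaccine on Day 62, that means the Day 63 and 67 samples but not Days 60 and 61. Antigen-specific readouts can stay in.
4. State that the Day 90 sample, like Cohort 3's Day 30 sample, remains outside the window.

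This needs a short addition to exclusion 9, one recorded item at existing visits and one analysis rule. It adds no visit or draw. The downside is that a few samples from a cohort of 35 may be set aside.

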## C. Study Design and Research Methods

### **Part A; Cohorts 1 and 2**

Seventy subjects with documented evidence of a HZ vaccine at least 5 years previously, divided equally between recipients of ZVL (Cohort 1) or RZV (Cohort 2) - 35 in each group - will be enrolled. Participation will consist of 4 visits over the course of 7-10 days in which blood is drawn, a challenge dose of vOka is given, and a skin biopsy is obtained.

ID vOka challenge live attenuated VZV (as 1 dose of licensed ZVL; Zostavax) will be prepared by mixing 0.35 ml of accompanying diluent with the vaccine and injecting 2 side-by-side intradermal doses of 0.125ml each, for a total of 0.25 ml (about  $\frac{3}{4}$  of the normal dosage or 13,857 plaque forming units) intradermally in the non-dominant deltoid region, using a NanoPass MicronJet600 device, on D0. Blood (60 ml) will be drawn prior to vaccination (D0), and at Days 1, 3, and 7. A skin biopsy (4 mm punch biopsy) will be done at the injection site, on the first 20 subjects (up to 25, if replacements needed) in each vaccine group; five each of these 20 will be biopsied on Day 0, 1, 3, or 7 in the order in which the participants enter the study. The Day 0 biopsy will be done on the contralateral arm in the deltoid region prior to vaccination. Initially every subject enrolled will be required to do the biopsy; this is reflected in the consent. The consent form will be amended to remove references to the biopsy procedure once the number of subjects needed for the biopsies is reached.

Subjects in the ZVL group will be offered RZV vaccine (to comply with ACIP recommendations for shingles immunization), to be administered beginning  $\geq$  60 days after Day 0. If subject wishes to receive the RZV vaccine, 2 additional visits will be required at Day 60 and Day 120, increasing the duration of participation up to 4 months. Subjects will not be reimbursed for these visits but will receive the vaccine free of charge.

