### Specific Aims/Study Objectives

**Primary Objective 1.** To compare the rate of vOka DNAemia within 7 days after ID vOka administration in adults who received RZV or ZVL >5y before the challenge.

**Primary Objective 2.** To compare the rate of vOka DNAemia after ID vOka challenge at <1y after RZV or ZVL vaccination and at >5y after vaccination.

**Secondary Objective 3.** To identify the characteristics of the immune responses to RZV that predict the immunologic control of vOka DNAemia after ID vOka challenge at <1y and at >5y after vaccination.

*Note:* This will include studies to further define epitope-specific immune responses, and will measure transcript profile and epigenetic changes in immune cells following vaccination.

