### D. Description, Risks, and Justification of Procedures and Data Collection Tools

#### Risks

Zostavax- The risks are those associated with a licensed vaccine for people 50 years and older. Subjects will be given the relevant Vaccine Information Sheet (VIS).

ID vOka challenge (as 1 dose of licensed ZVL; Zostavax) –The intradermal route was previously studied in ~200 subjects without a noteworthy safety signal (13). The device for ID administration is licensed and was used in a prior study (COMIRB #11-1210). Some subjects will be receiving ZVL for the second time. There is no recommendation for a second dose of ZVL, but we completed a study (COMIRB #10-1461) in which 200 participants safely received a second dose of ZVL. Furthermore, ZVL is recommended after prior herpes zoster, which is analogous to re-exposure (as with our ID challenge) to the virus of herpes zoster. Very rarely, a brief, painless blistery rash limited to the site of injection may develop.

Shingrix – This vaccine will be administered according to the package insert. The risks are those associated with a licensed vaccine for people 50 years and older. Subjects will be given the Vaccine Information Sheet (VIS).

As with all vaccines or drugs, rarely an allergic reaction could occur – a rash, hives or even difficulty breathing.

Risk of receiving multiple shingles vaccines – two doses of RZV have been safely administered to prior ZVL recipients, and also to individuals who had prior HZ. This was done prior to licensure and mentioned in the ACIP recommendation, indicating no concern with an aberrant immune response in this setting.

Blood draws – 60 ml of blood will be taken at each blood draw for a total of 240 ml in 1 week for subjects in Cohorts 1, 2, 3 and 4. Subjects in Cohort 3, receiving ZVL, will have a total of 540 ml drawn over the course of the study. Subjects in Cohort 4, receiving RZV, will have a total of 600 ml drawn, over the course of the study. Neither will have more than 240 ml drawn in a week. The risks of phlebotomy are minimal and include pain, swelling, bruising, or infection around the vein, although this is very uncommon.

Punch biopsy – The skin biopsy will be taken at the ID vOka challenge site (except for Day 0 participants, in which case it will be done on the contralateral arm). The area will be numbed; then a punch biopsy device will be pressed into the skin removing a small circle of skin.

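### In each >5y cohort, 10 of 35 participants have the challenge site biopsied on Day 1 or 3, none in the <1y cohorts do, and Objective 2 has no analysis to separate biopsy from interval

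*Combined protocol and SAP*

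**What the plan says.** Section IV.C (Part A) enrols 70 people vaccinated at least 5 years earlier, "divided equally between recipients of ZVL (Cohort 1) or RZV (Cohort 2) - 35 in each group - will be enrolled". On biopsies it says: "A skin biopsy (4 mm punch biopsy) will be done at the injection site". This covers the earliest 20 entrants per vaccine group, with replacements allowed up to a total of 25. As to timing, "five each of these 20 will be biopsied on Day 0, 1, 3, or 7". The Day 0 biopsy is on the other arm, before the challenge. Section IV.D (Risks) confirms the location for the other days: "The skin biopsy will be taken at the ID vOka challenge site". Blood is drawn on Days 0, 1, 3 and 7. Neither the text nor the schedule of events states whether blood or biopsy comes first on a shared day.

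In Part B, Cohort 3 is challenged and "followed by visits 1, 3, and 7 days later at which blood is drawn". Cohort 4 has the same post-challenge pattern (Days 241, 243 and 247). Neither the Part B text nor its schedules contain a biopsy.

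Primary Objective 2 is "To compare the rate of vOka DNAemia after ID vOka challenge at <1y after RZV or ZVL vaccination and at >5y after vaccination", so it sets Cohorts 3 and 4 against Cohorts 1 and 2. Section IV.G plans logistic regression on vaccine group with adjustment for confounders; the examples given are two age variables, sex and race. Its secondary analyses take duration as the last PCR-positive day and magnitude as peak viral load. It names no biopsy term and no biopsy sensitivity analysis. Section IV.F mentions the biopsy only as an obstacle to recruitment.

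**The concern.** The intradermal challenge is meant to mimic viral replication in skin, and DNAemia is the readout of that replication. A punch through the injection site on Day 1 or 3 removes part of the source while the endpoint is still being measured. It happens on only one side of the interval contrast. If the punch changes later DNAemia at all, part of any <1y versus >5y difference, or of its absence, belongs to the biopsy, and the planned analysis would not show how much.

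If the punch lowers DNAemia, the >5y rates are pulled down. That works against detecting ZVL waning, and it could hide RZV waning if there is any. If the punch raises DNAemia, for example through tissue disruption, it would exaggerate waning. Duration and peak load are more vulnerable than the yes/no endpoint: a participant already positive before the punch stays positive, but the last positive day and the peak can still move.

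**Working it through.** **Inputs.** 35 per cohort; biopsies 5 each on Days 0, 1, 3 and 7 in Cohorts 1 and 2, none in Cohorts 3 and 4 (section IV.C). ZVL rate 86%, two-fold reduction with RZV, hence 43%; 19 per group for 80% power at alpha 0.05 (section IV.G). The 7-day window is stated for Objective 1; I take it to apply to Objective 2, whose last post-challenge draw is also nominally 7 days after challenge.

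**The plan's own figure.** Two-sided test of two proportions, pooled variance under the null, no continuity correction: mean rate 0.645, so n = [1.96 × √(2 × 0.645 × 0.355) + 0.8416 × √(0.86 × 0.14 + 0.43 × 0.57)]² / 0.43² = 18.2, rounded up to 19. This matches. It is a power figure for RZV versus ZVL; the documents give no rates or power for Objective 2.

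**Who is affected.** Day 0 biopsies do not touch the challenge site, and Day 7 biopsies fall at the last scheduled draw. That leaves 5 + 5 = 10 of 35 = 28.6% in each >5y cohort, against 0 of 35 in each <1y cohort. The other 25 have no challenge-site punch before Day 7. If all five permitted replacements also fell on Day 1 or 3, the upper bound would be 15/35 = 42.9%.

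**Illustrative shift.** Let p be the true rate, r an assumed relative risk reduction in the 10, and e the share of their risk still open at the time of the punch. With no true interval effect, the observed >5y rate is p × (1 − (10/35) × r × e).

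For e = 0.5, assume that first positives are spread evenly over Days 1, 3 and 7 and that same-day blood comes first. A Day 1 punch then leaves 2/3 of the risk open and a Day 3 punch leaves 1/3, an average of 1/2.

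| r (assumed) | ZVL 86%, e = 1 | ZVL 86%, e = 0.5 | RZV 43%, e = 1 |
|---|---|---|---|
| 0 | 0 | 0 | 0 |
| 10% | −2.5 points (83.5%) | −1.2 | −1.2 |
| 25% | −6.1 (79.9%) | −3.1 | −3.1 |
| 50% | −12.3 (73.7%) | −6.1 | −6.1 (36.9%) |

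For ZVL at 35 versus 35, the chance of a significant result in the biased direction, nominally 2.5%, becomes about 4.7%, 10% and 25% for shifts of −2.5, −6.1 and −12.3 points.

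An effect in the other direction is capped for ZVL by the ceiling: (100 − 86) × 10/35 = +4 points.

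**Objective 1.** Both cohorts have the same biopsy plan. At r = 50%, e = 1, the contrast becomes 73.7% versus 36.9%. The ratio stays 2.0, the difference shrinks from 43 to 36.9 points, and power at 35 per group is about 89% instead of 98%.

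**Cost of excluding the 10.** For Objective 1 at 25 versus 25, power for 86% versus 43% is 91% by formula and 92% by simulation. For Objective 2, with similar rates in both groups, the standard error grows by √(1/25 + 1/35) / √(2/35) = 0.262/0.239 = 1.10, about 10%.

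**The case against.** The strongest reply is that the biopsy effect is only assumed. No passage says that a 4 mm punch alters DNAemia. The challenge is two adjacent 0.125 ml injections, and the punch takes only part of that area. With an assumed depth of 2 to 4 mm, the core is π × 2² × 2 to 4 = 25 to 50 mm³, or 10% to 20% of the 250 mm³ injected if virus stays evenly within that volume. A 10% to 20% risk reduction with half the risk exposed shifts the ZVL rate by only 1.2 to 2.5 points. This stands: 12 points is the far end of an illustration, not an estimate.

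It is also fair that the covariate list in section IV.G is open-ended, so a biopsy term is allowed. Allowed is not the same as planned, and nothing commits the sponsor to it. Part A and Part B are non-randomised groups that differ in other ways too. That is true, but this difference is one the trial itself introduces and can examine with data it already collects.

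Several stronger readings are tempting and not supported:

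- A reader might infer that Objective 2 is wholly confounded. It is not, because 25 of 35 per >5y cohort are unaffected before Day 7.
- A reader might infer that the bias favours Hypothesis 2. A lowering effect opposes the ZVL half of that hypothesis. For RZV with no true change it would make the later cohort look better, not equal; RZV would look falsely stable only if it truly waned.
- A reader might infer that allocating biopsy day by order of entry ties it to calendar time or assay batch. The documents describe no batching, and the wording may simply mean rotation through the days.

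**Conclusion.** The point holds in a limited form. The imbalance is fixed by design: 29% of each >5y cohort against none of each <1y cohort have a procedure at the site of viral replication before ascertainment ends. The plan has no analysis that would separate it from interval since vaccination. Size and direction of any biopsy effect are unknown, and zero is possible. For a lowering effect of 10% to 50%, the ZVL >5y rate would fall by about 2.5 to 12 points with all risk exposed, or about 1 to 6 points if those already positive are unaffected. These figures rest on the plan's 86%, on no true interval effect, and on assumed values of r and e. Duration and peak load carry more of the risk than the yes/no endpoint. For Objective 1 the documents do not support a claim of bias between vaccines; only dilution of the difference is possible. This is an inexpensive improvement that should be made, not a flaw that invalidates the comparison.

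**What to change.** Add to section IV.G a pre-specified sensitivity analysis for Objective 2, covering DNAemia, duration and peak load, that excludes participants with a challenge-site biopsy on Day 1 or 3. Report the same analysis as support for Objective 1. State that the Objective 2 conclusion will be qualified if the full and restricted estimates differ materially. Exclusion depends on biopsy day, which the plan sets by order of entry and not by outcome.

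State in section IV.C that blood is drawn before the biopsy when both fall on the same day. This protects the same-day sample on Days 1 and 3 and keeps the five Day 7 biopsies clearly among the 25 unaffected.

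A biopsy covariate may be added but should not be the main remedy. At 86%, the 10 early-biopsied ZVL participants are expected to yield 10 × 0.14 = 1.4 non-events, and the chance of none is 0.86^10 = 22%, so the planned Wald intervals may be unreliable. There is no need to change how biopsy days are allocated, which would do nothing about the imbalance between Parts A and B.

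The cost is one paragraph in the analysis plan, one sentence on the order of procedures, and a restricted analysis that is slightly less precise.
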